Creative Arts Therapy (CAT) in the Center for Cancer and Blood Disorders

[name]

Associate Professor, Pediatrics

University of Colorado

Children's Hospital Colorado

NCT04208243

COMIRB Protocol

PROTOCOL #: 10-1028

**COLORADO MULTIPLE INSTITUTIONAL REVIEW BOARD
[name] [contact]
[contact]**

Project Title: Creative Arts Therapy (CAT) in the Center for Cancer and Blood Disorders

Principal Investigator: [name], MSN, CPNP

Co-Investigators: [name], CPNP

Version Date: 5/10/2019

I. Hypotheses and Specific Aims

The purpose of the study is to evaluate the effectiveness of Creative Arts Therapy (CAT) on pediatric patients undergoing chemotherapy in the Infusion Center at Children's Hospital Colorado Center for Cancer and Blood Disorders. Findings from a previous pilot study support the hypothesis that CAT may improve quality of life (QOL), resiliency, physical posture, and emotional response to pain of pediatric oncology patients undergoing chemotherapy.

Specific aims include:

- a. Does CAT improve the child's reported QOL?
- b. Is the child's resiliency enhanced by CAT?
- c. Does CAT influence the physical posture of the child?
- d. Does CAT impact the child's emotional response to pain?
- e. Are patients, families, and staff satisfied with the CAT program?

II. Background and Significance

Although survival rates of children with cancer are improving, their QOL is known to be poorer than their healthy peers. As survival rates of pediatric cancer now approach 85%, the need for quality psychosocial care including creative arts has increased (Askins & Moore, 2008). Oncology patients are known to have significant morbidity during treatment as a result of the surgery, radiation and chemotherapy, but little is published on the day to day effects of treatment on the quality of life of pediatric oncology patients (Banks, 2008). Tremolada et al looked at parental perception of QOL in newly diagnosed children with leukemia and found that increasing the knowledge of QOL may improve communication and psychosocial care during initial treatment for leukemia (2010). In addition, quality of life among adolescents with cancer may be worse during treatment than for those not currently on therapy (Ward-Smith et al., 2007). Another study has shown that interventions to promote happiness may be a good predictor of QOL in adolescent cancer survivors (Bitsko et al., 2008).

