CAT is a subset of CAM that may improve QOL. CAT is a broad term encompassing the modalities of dance/movement, music, art. Bringing creativity into health care is a current trend in oncology nursing and throughout the medical professions (Garland et al., 2007; Lane, 2006; Petterson, 2001; Strickland, 2008). There is a growing body of literature establishing the use

of CAT, but the studies use non-standardized tools, small sample sizes, adult populations, and non-rigorous designs. Much of the work on CAT in cancer patients studies adult populations using qualitative measures (Forzoni et al, 2010; Jones et al., 2009; Visser, et al, 2008; Bar-Sela, et al., 2007; Nainis et al., 2006). Other work looked at the family caregivers of patients with cancer and showed significantly reduced stress, anxiety, and increased positive emotions after a creative arts intervention (Walsh et al., 2004). Randomized controlled studies are in the literature and have shown improvement in QOL, but only for the population of women with breast cancer (Oster et al, 2006; Monti et al, 2006; Svensk et al, 2009; Thyme et al, 2009). Music was shown to decrease heart rate in children with leukemia, but the therapeutic aspects were not studied (Kemper et al., 2008). The literature is rich with other examples of types of music, art, movement therapies that may improve QOL in adult and pediatric oncology patients, but there are few rigorous studies to document the importance of CAT during the cancer treatment (Sencer et al, 2007; Dibell-Hope, 2000; O'Callaghan et al, 2007; Robb et al, 2003; Barrera, 2002; Hilliard, 2006).

Therefore, a pilot study of CAT on the QOL of pediatric brain tumor patients used a mixed-model approach with a randomized, controlled phase comparing CAT to a control. Pre- and post- measurements using the PedsQL showed statistically significant improvement on Parent report of child's hurt (problems with having a lot of pain), $p=0.03$ and Parent report of child's nausea (becoming nauseated while thinking about medical treatment), $p=0.0061$. The second non-randomized phase pre- and post- tested any child in group session of CAT. The subjects showed improved mood with statistical significance on the Faces Scale ($p < 0.01$), and patients were more excited ($p < 0.05$), happier ($p < 0.02$), and less nervous ($p < 0.02$) on the Emotional Responses Checklist (Madden et al, 2010).

Rationale

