The instruments have been successfully employed in several small studies of children with cancer (Bhat, 2005; Meeske et al, 2004). The PedsQL has been shown to be the most responsive to change when compared with other measures of QOL used with children undergoing chemotherapy (Banks et al, 2008; Klaassen et al, 2010).

2. *The Resilience Scale (RS)*

The RS-14 is a 14-item scale using a 7-point rating (1-7). The construct of resilience is measured by two factors: personal competence and acceptance of self and life. Wagnild and Young have completed psychometric testing that established internal consistency reliability and concurrent validity (Wagnild & Young, 1993). Many studies have validated that the scale may be used with samples of any age or ethnic background (Ahern et al, 2006), but it is written at a 6th grade level. The authors who developed the tool are currently using it in adolescents (personal communication, 5/25/10). Given that it is expected that half the population of this study will be teenagers, this tool will be used with subjects ages 12 and over to obtain initial data on CAT's effect on resilience.

3. *Faces Scale*

The Faces Scale has been used for evaluating emotional responses to pain on children 3-17 years old. It is a one page form with nine faces in order of happy to upset. Numerical values are given to each face as determined by childrens' perspectives for an affective value by asking 200 children to directly scale the feelings depicted by the faces. Consistent rating was measured by children over 5 years regardless of age, gender, or health status (McGrath, 1990). The scale is a facial affective scale and has been integrated as a routine measure for management of acute, recurrent, and chronic pain (McGrath, 1990; McGrath et al., 1996). For children less than 3 years old, parents will be asked to complete the Faces Scale. Although this scale has been used for emotional response to pain, it is felt to be an appropriate measure for the emotional response to the discomfort and anxiety in the infusion room.

4. *Postural Measurement*

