- Hematology or other patients in the infusion center
- Patients who have previously received more than 2 sessions of CAT in the infusion center
- Non-English speaking patients

3. Study Design

A repeated measures design will be used with each patient serving as his/her own control.

Any Oncology patient in the CCBD who has not previously received more than two sessions of CAT in the outpatient unit and who will be receiving approximately weekly infusions of at least one hour in the infusion center will be identified by a research assistant. The study will be explained to the patient/family and informed consent will

be obtained by the principal investigator or the research assistant. A demographic form will be completed including the information of diagnosis, age, treatment, educational level of parents, zip code, prior experience with art, music, movement.

The intervention will consist of approximately weekly CAT in the infusion center during cancer therapy. The interventionist is a Master's prepared, licensed dance/movement therapist who is experienced in music and art therapies as well. The CAT includes dance/movement such as playing with a parachute, simple yoga breathing and postures, and work with physioballs. The music includes singing, listening to music, and playing instruments. The art consists of drawing, finger painting, working with clay. The CAT may occur in individual sessions in private infusion rooms, or in groups in the middle of the infusion center. The CAT is not only a distraction, but also a therapeutic process addressing the stressors of cancer and its treatment. The "dose" of CAT will be recorded (number and type of sessions) and will be factored into the analysis.

The subjects and/or parents will be tested with all instruments before the intervention, and approximately every 30 days for no less than 3 months and a maximum participation of 6 months. Treatment time points will be at least 30 days apart. Because some subjects are not scheduled to come into the clinic every 30 days for SOC appointments, they are unable to complete 3 sessions of CAT in a 3 month time period. For those subjects who are scheduled to come into clinic every 1-2 months for SOC appointments, study participation may take up to 6 months. This 6 month time period would allow for the completion of 4 different time points of CAT.

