The testing will take place in an exam room after vital signs have been completed upon intake to the clinic. The trained research assistant, trained RN, or PI will administer the questionnaires. The PedsQL includes a subject report (ages 5 and over) and a parent report. The Resilience Scale is a self-report and will be used for ages 12 and over. The Faces Scale will use parent report for ages less than 5 and self-report for ages 5 and over. In order to confirm consistency, the posture measure will be completed by the PI (nurse practitioner) or registered nurse on the study after training with the manual included with the inclinometer tool.

Off Study Criteria

1. Subject discontinues CAT
2. Unable to complete 4 time points in 6 months

C. Description, Risks and Justification of Procedures and Data Collection Tools

The anticipated risks include psychological distress incurred by completing the outcome measure questionnaires as well as the therapeutic process. This risk will be minimized by the presence of the Master's prepared, experienced dance/movement therapist. The patients' social workers through the clinic will be available during the intervention as well.

D. Potential Scientific Problems

Based on the pilot data, the anticipated scientific problem is slow accrual due to unforeseen events during the traumatic time of a new diagnosis in pediatric oncology. We are unable to randomize because CAT is standard of care for any patient in the infusion center and therefore we feel it is unethical to deny CAT to a control arm. Therefore, we will compare the subjects to themselves over time to look at longitudinal changes of CAT.

E. Data Analysis Plan

The primary outcome is Peds QL at approximately 3 months; secondary outcomes will be the Resilience Scale, Faces Scale, and postural measurement at approximately 3 months. A repeated measures analysis of variance will be used to analyze the primary and secondary outcomes. We will also use the repeated measures analysis of covariance with the addition of covariates, depending on their statistical significance, such as gender, age, cancer diagnosis, and previous exposure to arts/music/dance. All of the analysis will be adjusted for baseline measures.

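### The Faces Scale is justified by distress in the infusion room but given at clinic intake, so it supports claims only about affect at intake; its reporter rules also conflict

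*Combined protocol and SAP*

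**What the plan says.** Aim (d) in Section I asks: "Does CAT impact the child's emotional response to pain". Section IV.A.3 acknowledges that the Faces Scale has been used for emotional response to pain, and justifies it here because "it is felt to be an appropriate measure for the emotional response to the discomfort and anxiety in the infusion room".

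Section IV.B.3 sets the schedule: "The subjects and/or parents will be tested with all instruments before the intervention, and approximately every 30 days". It also fixes place and time, with no exception for the Faces Scale: "The testing will take place in an exam room after vital signs have been completed upon intake to the clinic". CAT is given somewhere else: "The intervention will consist of approximately weekly CAT in the infusion center during cancer therapy".

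The supporting pilot evidence is in Section II: "The second non-randomized phase pre- and post- tested any child in group session of CAT", with improvement on the Faces Scale at p < 0.01.

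Section IV.E makes the Faces Scale a secondary outcome at about 3 months, adjusted for baseline. Section IV.D describes the contrast as each subject compared with himself or herself over time.

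On who reports, Section IV.A.3 says: "For children less than 3 years old, parents will be asked to complete the Faces Scale". Section IV.B.3 says: "The Faces Scale will use parent report for ages less than 5 and self-report for ages 5 and over". Eligibility in Section IV.B.2 starts at age 3.

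**The concern.** The stated meaning of the score and the way it is collected do not match. The rating is taken in another room and, by reasonable inference, before that day's infusion and CAT. It does not capture the child's response in the infusion room, and it does not repeat the before-and-after contrast that produced the pilot result.

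What is at stake is the interpretation of aim (d). If the 3-month comparison is null, the data cannot separate two explanations: that CAT does nothing for distress during infusion, or that it helps there but the effect is not visible at a later intake. A reader relying on Section IV.A.3 would take the result as an answer about the infusion room.

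The reporter rules matter because each child is his or her own control. A change from parent to child report within a series enters directly into the within-child change.

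**Working it through.** **Figures available.** The only design calculation, in Section IV.E, concerns the PedsQL. It reproduces. For a two-sided two-sample t-test with 33 per group and alpha 0.017, the noncentrality at d = 0.813 is 0.813 × √(33/2) = 3.30 on 64 degrees of freedom. Power is 0.8001, and the detectable effect at 80% power is 0.8129. It has no bearing on the Faces Scale, for which the documents give no standard deviation, effect size or duration of effect. The timing question is therefore settled by comparing the sections.

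**Place and time**

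| Feature | Justification or pilot (II, IV.A.3) | As scheduled (IV.B.3) |
|---|---|---|
| Place | Infusion room; pilot in group CAT | Exam room |
| Moment | Response to discomfort and anxiety there; pilot before and after CAT | Clinic intake, after vital signs |
| Contrast | Pilot: within session | Baseline, then about every 30 days |

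That intake testing precedes the day's CAT is an inference: intake comes first, and CAT takes place later in the infusion center. On the approximately weekly schedule, the most recent CAT session is then about 7 days old. For the children Section IV.B.3 describes as attending every 1-2 months, it is about 30 to 60 days old.

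The main text gives no instruction asking the child to recall the infusion room. The form itself is Appendix 3, which is not in the text supplied, so such an instruction cannot be ruled out.

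**How many children could supply new data.** Section IV.B.1 plans 100 patients, says enrollment was reached in 2019, and allows 10 more. If 100 is the number reached, the additional patients are 10/(100 + 10) = 9% of the total. Earlier enrollees still within their maximum of 6 months would add to this; their number is not given.

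**Reporter rule**

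- Eligibility starts at age 3, so the under-3 rule in Section IV.A.3 applies to no eligible child. By implication it leaves ages 3 and 4 to self-report.
- Section IV.B.3 assigns ages 3 and 4 to parent report.
- Under Section IV.B.3, a child within 3 to 6 months of a fifth birthday at baseline switches reporter during participation.

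The age distribution is not given, so the size below is illustrative:

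- *Assumption A.* Half of 100 are teenagers (Section IV.A.2) and the other 50 spread evenly over the 10 years of age from 3 to 12, which is 5 per year. Ages 3-4: 2 × 5 = 10 children. Switchers: 5 × 0.25 to 5 × 0.5 = 1.25 to 2.5.
- *Assumption B.* All 100 spread evenly over the 16 years of age from 3 to 18, which is 6.25 per year. Ages 3-4: 2 × 6.25 = 12.5 children. Switchers: 6.25 × 0.25 to 6.25 × 0.5 = 1.6 to 3.1.

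On either assumption, roughly 10 to 13 children fall under the conflicting rules and about 1 to 3 would change reporter.

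**The case against.** The strongest reply is that the study asks a longitudinal question. Aim (d) does not specify change within a session, and Sections IV.D and IV.E compare children with themselves at about 3 months. Section IV.B.3 presents CAT as a therapeutic process and not merely distraction. An intake rating suits a search for sustained change and keeps same-day distraction out of it. The rationale in Section II promises a larger sample, broader inclusion and new outcomes; it does not promise to repeat the pilot's session-level test. All of this stands, and it is why the intake score should remain the outcome. It does not rescue the justification in Section IV.A.3, which names the infusion room.

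A reader might go further and infer that aim (d) is measured at the wrong moment, so that a benefit confined to the session would contribute nothing. The documents do not support that. They do not say how long a CAT effect lasts, and an intake score can register change in general or anticipatory affect.

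A reader might also conclude that within-visit change should replace the intake score. That would redefine a secondary outcome after the planned enrollment was reached and rest it on few children. With no control, it would also mix CAT with the progress of the infusion.

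On the reporter rules, it can fairly be said that Section IV.A.3 never expressly assigns ages 3-4 to self-report, and that its under-3 rule looks like leftover wording. That makes the conflict easy to repair. It does not show which rule was followed, and it leaves the switch at age 5 untouched.

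**Conclusion.** The mismatch is real and nothing elsewhere in the documents resolves it. As scheduled, the Faces Scale measures affect at clinic intake over months. It does not measure the infusion-room response named in Section IV.A.3 or the session-level change seen in the pilot. The loss of sensitivity cannot be quantified from the documents. The consequence is a limit on what the result can claim; the intake score remains usable for longitudinal change. The PedsQL primary outcome is unaffected.

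The reporter rules conflict for ages 3-4, and the rule in Section IV.B.3 confounds within-child change for any child who turns 5 during follow-up. The numbers are probably small, about 10 to 13 and 1 to 3 children respectively, but they rest on assumed age distributions. The conclusion on timing rests on two readings: that intake precedes the day's CAT, and that the form carries no instruction directing the rating to the infusion room.

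**What to change.** 1. **Relabel the outcome.** Keep the baseline-adjusted intake reading as the pre-specified secondary outcome for aim (d). Restate it in Sections IV.A.3 and IV.B.3 as affect at clinic intake, and say that a null result will not be interpreted as no effect of CAT on distress in the infusion room. This costs wording only.

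2. **Add supplementary ratings.** For the additional 10 patients and anyone still in follow-up, give the one-page form in the infusion room before and after CAT at each assessment visit. Report these as descriptive and uncontrolled. The cost is two more short forms per assessment visit, at most 2 × 4 = 8 per child over four time points. Someone must also be available in the infusion center to give them. Section IV.C already lists questionnaire distress as a risk, and few children will contribute.

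3. **Settle the reporter.** Reconcile Sections IV.A.3 and IV.B.3 into one rule for ages 3-4, and fix each child's reporter at the baseline assignment so that turning 5 does not cause a switch. For data already collected, record who reported at each time point and analyse within-child change from a consistent reporter. The cost is a check of existing forms and possibly the loss of a few ratings from the change analysis.

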Physical functioning and muscle strength are aspects of QOL that have been shown to be worse than healthy peers in children with cancer (Hartman et al., 2008). This aspect may also be affected by the central venous access lines placed in almost all pediatric cancer patients. Long-term central venous access is critical in pediatric cancer patients and the evolution of these devices has improved QOL in terms of pain and distress of venipuncture (Spagrud, 2008). The literature is rich with discussion of complications and risk of infection, but little is published about the effects on body image and QOL (Albanese, 1993; Nam, 2010). Anecdotally, patients have improved body awareness and posture (less kyphosis) after CAT. In addition, it has been postulated that increased kyphosis may correspond with psychosocial factors including anxiety, depression, and insecurity. Body awareness is a type of physical functioning that may be measured by kyphosis. Measuring posture with an inclinometer has been shown to be reliable, but further work is needed to establish validity (Lewis & Valentine, 2010). Piloting this tool may establish a way to physically measure an individual's sense of self by the way that he or she stands.

The use of complementary and alternative medicine (CAM) is one intervention that has been shown to improve QOL in this population. Current trends show increasing popularity of the use of CAM in even among children with cancer. Martel et al (2005) looked at prevalence of use of CAM in children. In their survey, almost 50% of the children used at least one type of CAM. Specifically to cancer, in 2009, Post-White et al used a survey of 281 patients to show that CAM was used in 59% of pediatric cancer patients versus 36% of general pediatric patients. The authors confirmed that children with cancer and other chronic illnesses use more CAM therapies than children seen in primary care clinics. Roth et al (2009) examined pediatric oncologists' perceptions of CAM and found that although they place importance in CAM, they lack time and knowledge to ask about patients' use of CAM. These authors recommend CAM research in pediatric oncology on modalities that could improve QOL.

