Thoracic kyphosis will be measured using two gravity dependent inclinometers (Isomed Inc.). Spinal processes will be determined by palpation by a registered nurse or pediatric nurse practitioner. The feet of the inclinometers will be placed over the spinal processes thought to be at T1, T2 and T12, L1. The measurements will be taken in relaxed standing and measured 3 times in succession. Clinical assessment of the thoracic kyphosis angle is considered essential in postural examination, but can be time

consuming when measured radiographically (Lewis, 2010). Lewis and Valentine studied intra-rater reliability in subjects with and without symptoms and found measurements of less than 1.7 degrees should be considered measurement error. The test-re-test reliability established excellent intra-rater reliability. Although validity of this measure is less studied, the measurement is thought to provide guidance of how much change of the kyphoscoliosis angle is a real consequence of intervention over time (Lewis, 2010).

5. Patient/Family Surveys

A brief ten minute written survey will be administered to subjects to ascertain level of satisfaction with the program.

B. Description of Population to be Enrolled: Study Design and Research Methods

1. Population

The Center for Cancer and Blood Disorders (CCBD) at Children's Hospital Colorado sees approximately 240 new Oncology patients each year. Approximately 45% of these patients receive vincristine, a chemotherapy agent that is known to affect physical functioning. In addition, about 25% of these patients receive steroids, another medication known to affect physical functioning and quality of life. About half of the new patients each year are anticipated to fit the inclusion criteria. Therefore, we expect approximately 100 eligible subjects per year, with a 50% attrition rate, for a total sample size of 100 subjects over a two year period.

Enrollment for this study was reached in 2019. At this time, an additional 10 patients will be allowed to enroll on study to help supplement the data.

2. Eligibility Criteria

Inclusion

- Center for Cancer and Blood Disorders (CCBD) patient with Oncology or Neuro-oncology diagnosis
- No more than 2 previous sessions of CAT as an outpatient in the CCBD
- English speaking
- Receiving outpatient chemotherapy, biotherapy, or transfusions in the infusion center approximately weekly for at least 3 months.
- Ages 3 to 18 years

Exclusion

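### Nothing keeps a child's CAT session count or earlier angles from whoever takes the judgment-dependent posture reading, so avoidable rater bias may enter this secondary outcome, chiefly its dose contrast

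*Combined protocol and SAP*

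**What the plan says.** **Who measures.** Section IV.B.3 (Study Design) says that "the posture measure will be completed by the PI (nurse practitioner) or registered nurse on the study after training with the manual included" with the device. The stated aim of that training is consistency. For the other instruments, "The trained research assistant, trained RN, or PI will administer the questionnaires".

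**How posture is read.** Section IV.A.4 (Postural Measurement) says that "Spinal processes will be determined by palpation by a registered nurse or pediatric nurse practitioner", and "The measurements will be taken in relaxed standing and measured 3 times in succession". It also reports that a reliability study "found measurements of less than 1.7 degrees should be considered measurement error".

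**Who delivers CAT.** Section IV.B.3: "The interventionist is a Master's prepared, licensed dance/movement therapist who is experienced in music and art therapies as well". The therapist is not among the listed assessors. Testing takes place in an exam room at clinic intake. CAT itself may be given in private rooms or in groups in the open infusion center.

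**How the data are used.** Each child is his or her own control. The number and type of sessions are recorded and enter the analysis. Section IV.E makes PedsQL primary and posture secondary, and expects a positive dose-response relationship across three session-count groups.

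**Prior expectation.** Section II: "Anecdotally, patients have improved body awareness and posture (less kyphosis) after CAT".

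**Masking.** The document says nothing on masking assessors to session count, earlier scores or earlier angles. Section IV.D explains why there is no randomization. It does not discuss masking of assessment.

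**The concern.** CAT cannot be masked, but assessment can be masked in part, and the plan has no rule for it. Posture is the only efficacy outcome that is not self- or parent-reported, so it is where a rule about the assessor has most to offer. An assessor who knows how many sessions a child has had, or who sees last month's angle, may choose landmarks, accept a stance or read the dial differently.

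Training from the manual makes readings repeatable. It does not prevent a shift in one direction, since a consistent rater can be consistently biased. There is no control arm in which such a shift would cancel. If the shift varies with known session count, it enters the dose contrast directly and could be mistaken for dose-response.

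**Working it through.** **1. What the text permits.**

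| Element | Source | Bearing |
|---|---|---|
| PI or study RN takes the reading | IV.B.3 | PI readings are permitted, not required |
| Landmarks palpated, relaxed stance | IV.A.4 | Steps that need judgment |
| Three readings in succession | IV.A.4 | Nothing hides one reading before the next |
| Session count recorded and analysed | IV.B.3 | Exposure that an assessor could know |
| Separate therapist, exam-room testing | IV.B.3 | Makes partial masking feasible |
| Open group sessions | IV.B.3 | Makes complete masking unlikely |

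Reading all sections for a rule that withholds session counts or earlier results finds none. The gap is therefore one of silence. Three successive readings, if averaged, reduce random error but leave a shift common to all three unchanged.

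**2. The plan's own design figure.** Section IV.E gives 33 children per group, 80% power, alpha 0.017 and a minimum effect size of 0.813. A two-sided independent two-sample t-test (noncentral t, 64 degrees of freedom) gives 0.8129, so the figure reproduces. It was derived for PedsQL. Only the group size and alpha are borrowed below.

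**3. Dose contrast, illustration.** The documents give no posture SD and no rater-bias figure, so the shift b (in SD units) is assumed. With no true effect:

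- Noncentrality = b × √(33/2) = b × 4.062.
- Two-sided critical t at alpha 0.017 with 64 df = 2.451.
- False-positive rate = probability that |t| exceeds 2.451.

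| Assumed b | Noncentrality | False-positive rate per comparison |
|---|---|---|
| 0 | 0 | 1.7% |
| 0.1 | 0.406 | 2.6% |
| 0.2 | 0.812 | 5.6% |
| 0.3 | 1.219 | 11.6% |
| 0.5 | 2.031 | 34.4% |

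If the SD is between 3 and 8 degrees (assumed), b = 0.2 is 0.6 to 1.6 degrees (0.2 × 3 to 0.2 × 8). Throughout that range it is below the 1.7 degrees that the protocol cites as measurement error.

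**4. Before-after contrast, illustration.** Assume n = 100, two-sided alpha 0.05, no true change and a 1-degree shift. Noncentrality = (1/SD) × √100, and the critical t with 99 df is 1.984.

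| Assumed SD of change (degrees) | Noncentrality | Declared significant |
|---|---|---|
| 3 | 3.33 | 91% |
| 5 | 2.00 | 51% |
| 8 | 1.25 | 24% |

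These rates concern statistical significance only. They do not apply the 1.7-degree threshold, and by that threshold a 1-degree mean change would not be read as real. The proposed rule also helps little here, because an assessor can still tell baseline from follow-up.

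**5. How much data a new rule reaches.** Section IV.B.1 says that enrollment was reached in 2019 and allows 10 more patients. If the planned 100 were enrolled, that is 10/110, about 9% of patients, plus any visits still outstanding.

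**The case against.** **The plan is silent; it does not direct unmasked assessment.** This stands. It allows someone other than the PI for every measure, separates the assessors from the therapist, and tests away from the infusion area. A reader might infer that the PI does know each child's sessions and earlier results, or that children answer the person who runs the CAT programme. The document says neither. It permits such knowledge and does nothing to prevent it.

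**Direction and size are unknown.** This also stands. A reader might infer that the bias must favour CAT, given the expectation stated in Section II. But an earlier angle in view may equally anchor the rater to it and dilute change. No rater-bias figure is given, and no change has been reported that a shift could explain.

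**Masking would be incomplete, and the RN may know as much as the PI.** This stands in part. Group sessions are visible, families may mention them, and nothing shows that an RN knows less about dose. The gain therefore comes mainly from withholding the log and earlier angles, and less from the change of person.

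**Questionnaires would gain little.** Largely right. PedsQL, the Faces Scale and the Resilience Scale (ages 12 and over only) are answered by children or parents who know that CAT was given. A reader might infer that masking the administrator would protect the primary outcome. It would leave respondent expectation in place. Nor would posture become free of expectation, since the child's own stance is part of the measurement.

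**It is late.** This limits the reach of new procedures, but not of the sensitivity analysis or the stated limitation.

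**Conclusion.** The point holds as a low-cost improvement to a secondary outcome. The plan lets the PI or a study RN take a posture reading that needs judgment, and it does not keep the session count or earlier angles from that person. Rater expectation or anchoring may therefore affect posture, chiefly the comparison across session counts.

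That no safeguard exists rests on the text alone. The false-positive rates (5.6% at 0.2 SD, 11.6% at 0.3 SD, against a nominal 1.7%) rest on assumed shifts and show only that a small systematic difference could matter. They do not estimate what happened in this study. The documents do not support a conclusion that the posture results are biased, that any bias favours CAT, or that the primary PedsQL analysis is compromised by this route.

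**What to change.** **Section IV.B.3**, for the additional patients and all remaining visits:

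- The study RN takes posture readings where possible.
- Each visit uses a fresh form on which no earlier angles or scores are visible.
- The CAT session log is not shown to the assessor before testing.
- The person who took each reading is recorded.
- As a preference, the research assistant or RN administers the questionnaires where possible.

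**Section IV.E:**

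- Where the assessor is identifiable, including in data already collected, repeat the posture analysis without PI readings and report it beside the main result. If past records do not identify the assessor, say so.
- State as a limitation that assessors, children and parents were not masked.

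**Cost.** Protocol wording, a form-handling rule and one sensitivity analysis. No new role is needed. Scheduling is less flexible on days when only the PI is available, and the assessment procedure changes partway through the study, which the report should mention. Masking stays partial because baseline and follow-up can be told apart, group CAT is visible in the infusion center, and most data were probably collected before the rule.
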